## 11.2 ADVERSE EVENTS

Grades of AEs will be assigned according to the CTCAE, Version 4.03. AEs will be coded to the system organ class (SOC) and PT level using the Medical Dictionary for Regulatory Affairs (MedDRA) Dictionary Version 23.0. Treatment-emergent AEs (TEAEs) will be summarized. All AEs will be listed regardless of when they were reported.

Summaries of TEAEs will count the number of subjects, not the number of events; that is, subjects with multiple occurrences of the same TEAE will be counted once.

An overview summary of TEAEs, including counts and percentages of subjects with: any TEAEs; TEAEs of CTCAE Grade 3 or above; TEAEs related to any study treatment; TEAEs related to IMO-2125; TEAEs related to ipilimumab; TEAEs related to any study treatment of CTCAE Grade 3 or above; TEAEs related to IMO-2125 of CTCAE Grade 3 or above; TEAEs related to ipilimumab of CTCAE Grade 3 or above; immune-related TEAEs (see [Table 2](#) in Section 11.5 for the list of AEs); immune-related TEAEs of CTCAE Grade 3 or above, immune-related TEAEs related to any study treatment; immune-related TEAEs related to IMO-2125; immune-related TEAEs related to ipilimumab; TEAEs leading to IMO-2125 discontinuation; TEAEs leading to ipilimumab discontinuation; TEAEs leading to dose modifications (i.e., dose interruptions or dose reduction); SAEs; SAEs of CTCAE Grade 3 or above; SAEs related to any study treatment, SAEs related to IMO-2125; SAEs related to ipilimumab; fatal AEs; fatal AEs related to any study treatment, fatal AEs related to IMO-2125; and fatal AEs related to ipilimumab will be produced.

The frequency and percentage of TEAEs (all grades) will be summarized in descending order of total incidence by SOC and PT. In the SOC row, the number of subjects with multiple events under the same SOC will be counted once. In addition, a separate table for the frequency and percentage of TEAEs (all grades) in descending order of total incidence by PT will be generated. Summaries of TEAEs of CTCAE Grade 3 or above will be produced similarly in descending order of total incidence by PT.

A separate summary will be provided for study treatment-related TEAEs for each study treatment in descending order of total incidence by PT. Treatment-related TEAEs are those

Idera Pharmaceuticals, Inc.  
Statistical Analysis Plan  
Protocol Number: 2125-MEL-301

---

deemed as ‘possibly related’ or ‘related’ to the study drug by the investigator. In the IMO-2125 + ipilimumab arm, TEAEs related to either study treatment will be reported. Missing relationship to study treatment will be imputed as described in [Section 8.1.1](#). Similar analysis will be repeated for Grade 3 or above treatment-related TEAE by PT.

In addition, a summary of number and percentage of subjects with any TEAE by maximum grade will be produced. TEAEs will be sorted by PT in descending order of total incidence in the IMO-2125 + ipilimumab arm. Each summary will report the number of subjects with at least one TEAE and the PT reported. Subjects are counted once for each unique PT under the maximum grade. A similar analysis will be repeated for treatment-related TEAE by PT and maximum grade. In the IMO-2125 + ipilimumab arm, TEAEs related to either drug will be reported. This analysis will also be repeated for TEAE related to IMO-2125 and for TEAE related to ipilimumab in both the combination arm and ipilimumab alone arm.

Cumulative TEAEs at 3, 6, 9, and 12 months from first dose will include all TEAEs with a start date on or before 3, 6, 9, or 12 months from the first dose date. The calculation for the days in x months is  $x*(365.25/12)$ ; the cutoff date for x months is therefore (first dose date +  $x*(365.25/12)$ ). Incidence of subjects experiencing TEAEs up to the specified cut point from first dose will be summarized by PT and maximum grade. A similar analysis will be repeated for treatment-related TEAEs up to the specified cut point from first dose.

Incidence of TEAEs will be summarized by MedDRA PT and time of onset relative to the first exposure of the study drug by 3-week interval during the treatment period. The first onset interval will start at the first dose date and end on the 21st day (Weeks 1-3); the second interval will start on the 22nd day and end on the 42nd day (Weeks 4-6); the third interval will start on the 43rd day and end on the 63rd day (Weeks 7-9); the fourth interval will start of the 64th day and end on the 84th day (Weeks 10-12); the fifth interval will start from the 85th day and end on the 105th day (Weeks 13-15); the sixth interval will start from the 106th day and end on the 126th day (Weeks 16-18); the seventh interval will start from the 127th day and end on the 147th day (Weeks 19-21); and the last will start on the 148th day and end on the 168th day (Weeks 22-24). Adverse events will be assigned to onset categories according to the relative study day when the AE started. AEs with incomplete onset dates will be excluded from this analysis. For subjects who experienced the same AE multiple times and within different onset categories, the event will be counted once in each of the categories in which it started. For each onset category, AE incidences will be calculated by dividing the number of subjects who had each AE during that onset category by the number of subjects who have not dropped out or died at the start of the onset interval. For example, for onset category Weeks 4-6, the denominator will be the number of subjects who have not dropped out or died by the start of Weeks 4-6 interval and were therefore in the risk set for that interval.

Idera Pharmaceuticals, Inc.  
Statistical Analysis Plan  
Protocol Number: 2125-MEL-301

---

All AEs will be listed. This listing will include treatment arm, age, sex, start date and study day, end date and study day, grade, serious (yes or no), irAE (yes or no), relationship to treatment (yes or no), action taken, outcome, and preferred and verbatim terms.

The following summaries will be provided:

- Overall Summary of Treatment-Emergent Adverse Events
- Treatment-Emergent Adverse Events by System Organ Class and Preferred Term
- Treatment-Emergent Adverse Events by Preferred Term
- Treatment-Emergent Adverse Events by Preferred Term and Maximum Grade
- Treatment-Related Treatment-Emergent Adverse Events by Preferred Term (including Treatment-Related, IMO-2125-Related, and Ipilimumab-Related)
- Treatment-Related Treatment-Emergent Adverse Events by Preferred Term and Maximum Grade
- Grade 3 or Above Treatment-Emergent Adverse Events by Preferred Term
- Grade 3 or Above Treatment-Related Treatment-Emergent Adverse Events by Preferred Term
- Cumulative TEAEs at Three Months by Preferred Term and Maximum Grade
- Cumulative TEAEs at Six Months by Preferred Term and Maximum Grade
- Cumulative TEAEs at Nine Months by Preferred Term and Maximum Grade
- Cumulative TEAEs at Twelve Months by Preferred Term and Maximum Grade
- Cumulative Treatment-Related TEAEs at Three Months by Preferred Term and Maximum Grade
- Cumulative Treatment-Related TEAEs at Six Months by Preferred Term and Maximum Grade
- Cumulative Treatment-Related TEAEs at Nine Months by Preferred Term and Maximum Grade
- Cumulative Treatment-Related TEAEs at Twelve Months by Preferred Term and Maximum Grade
- TEAE Incidence by Time to Onset in 3-Week Interval During the Treatment Period

The following listings will be provided:

- All Treatment-Emergent Adverse Events
- Adverse Events Between Signing Consent and the Start of Study Treatment

While pregnancy itself is not considered to be an AE or SAE, any pregnancy complication or elective termination of a pregnancy for medical reasons will be recorded as an AE or SAE as described in the protocol. If any subject or subject's partner becomes pregnant while on the

Idera Pharmaceuticals, Inc.  
Statistical Analysis Plan  
Protocol Number: 2125-MEL-301

---

study, the information will be included in the CSR narratives and no separate table will be produced.

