9.3.3. Administration

Subjects will be randomized (1:1) to receive either:

1. Arm A – ipilimumab 3 mg/kg i.v. at Weeks 1, 4, 7, and 10
or
2. Arm B – IMO-2125, 8 mg intratumorally at Weeks 1, 2, 3, 5, 8, 11, 16, 20, and 24 in combination with ipilimumab 3 mg/kg i.v. at Weeks 2, 5, 8, and 11

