### **8.2.7 Treatment Emergence Flag**

A treatment emergence flag will be derived based on the AE start date (and time if available) to determine an AE occurred before or after first dose date of either study drug. If an AE occurred prior to the first dose date, the AE will be designated as not treatment emergent. If an AE occurred after the first dose date, the AE will be designated as treatment emergent. If an AE occurred on the same date or the same date/time of first dose date(time), the AE will be designated as treatment emergent unless 'NOT APPLICABLE' was recorded for the action taken with both study drugs for the combination arm or the AE was considered related to the either study drug. Similar rules will be applied to the ipilimumab alone arm.

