### **11.4 ADVERSE EVENTS LEADING TO DISCONTINUATION OF STUDY TREATMENT (WITHDRAWAL), DOSE INTERRUPTIONS, OR DOSE REDUCTIONS**

Dose reductions are only permitted for subjects enrolled under Protocol Version 2.0. TEAEs leading to dose interruption and dose reduction will be listed. The following category of TEAEs will be summarized by PT:

- TEAEs Leading to Permanent Discontinuation of IMO-2125 by Preferred Term

Idera Pharmaceuticals, Inc.  
Statistical Analysis Plan  
Protocol Number: 2125-MEL-301

- 
- IMO-2125-Related TEAEs Leading to Permanent Discontinuation of IMO-2125 by Preferred Term
  - TEAEs Leading to Permanent Discontinuation of Ipilimumab by Preferred Term
  - Ipilimumab-Related TEAEs Leading to Permanent Discontinuation of Ipilimumab by Preferred Term

The following listings will be provided:

- TEAEs Leading to Dose Interruption or Dose Reduction
- TEAEs Leading to Treatment Discontinuation

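### The adverse-event overview gives dose modification as one row with no drug named, so it cannot show whether adding IMO-2125 leads to more held ipilimumab doses

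*SAP*

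**What the plan says.** SAP 11.2 lists the rows of the overview together. Two rows for discontinuation come first, one for IMO-2125 and one for ipilimumab; the next row is "TEAEs leading to dose modifications (i.e., dose interruptions or dose reduction", which names no drug. The rows for related TEAEs in the same overview are also split by drug. The counting unit is the subject: "Summaries of TEAEs will count the number of subjects, not the number of events".

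SAP 11.4 tabulates permanent discontinuation by drug, but for the milder actions it says only that "TEAEs leading to dose interruption and dose reduction will be listed". In the SAP 16.2 output list, Table 14.3.2.1 is marked for the IDMC, the ORR analysis and the final analysis, and is starred as topline. The listing of interruptions and reductions (16.2.3.2.5) is marked for the ORR and final analyses only.

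Protocol 9.3.3 gives Arm A "ipilimumab 3 mg/kg i.v. at Weeks 1, 4, 7, and 10". Arm B receives "IMO-2125, 8 mg intratumorally at Weeks 1, 2, 3, 5, 8, 11, 16, 20, and 24" together with "ipilimumab 3 mg/kg i.v. at Weeks 2, 5, 8, and 11". Protocol 8.2.1 sets the treatment phase at 10 weeks in Arm A and 24 weeks in Arm B.

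**The concern.** Protocol 10.1.3.7 defines an interruption as a temporary halt or a skipped dose, so one can be recorded only while a dose is still planned. Arm B has more planned doses over a longer period. Under Protocol 9.3.4, IMO-2125 also continues when ipilimumab is stopped early for toxicity. An Arm B subject can therefore still enter the row after ipilimumab has ended, and an Arm A subject cannot.

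The row thus mixes the length of the schedule with tolerability. The question that isolates the effect of adding IMO-2125 is whether more subjects have ipilimumab held for an adverse event. Four infusions are scheduled in each arm, yet no planned table answers it. A reader of the overview could go wrong in either direction: take a schedule effect for toxicity, or dismiss a real excess of held ipilimumab doses as schedule. The IDMC receives this table and weighs benefit against risk throughout the study (Protocol 8.1.2).

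**Working it through.** The plan states no rate or expected count for this row, so there is no figure of its own to reproduce. The check asks what the row would show if the risk per dose were equal.

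**Inputs**
- Arm A: 4 infusions (Protocol 9.3.3).
- Arm B: 9 injections + 4 infusions = 13 administrations. Weeks 2, 5, 8 and 11 are all injection weeks, so these fall on 9 visits.
- The re-treatment criteria in Protocol 9.3.4 apply to each dose.
- Probability q that a given dose is modified for a TEAE: not in the documents. Assumed 1% to 10%, with every dose reached and doses independent.

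**Equal risk per dose.** The proportion of subjects with at least one modification is 1 − (1 − q)^n. For Arm B, n = 9 applies if both drugs are always held together, and n = 13 if each administration counts separately.

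| q | Arm A (n = 4) | Arm B (n = 9) | Arm B (n = 13) |
|---|---|---|---|
| 1% | 3.9% | 8.6% | 12.2% |
| 2% | 7.8% | 16.6% | 23.1% |
| 5% | 18.5% | 37.0% | 48.7% |
| 10% | 34.4% | 61.3% | 74.6% |

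For example, at 5%: 1 − 0.95^4 = 18.5%, 1 − 0.95^9 = 37.0%, 1 − 0.95^13 = 48.7%.

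**Lower risk for IMO-2125 doses.** With 5% per infusion and m per injection, Arm B is 1 − 0.95^4 × (1 − m)^9. This gives 35.1% at m = 2.5%, 25.6% at m = 1% and 18.5% at m = 0. Arm A stays at 18.5%.

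**Cross-check with the same adverse-event process in both arms.** Assume events arise at 0.05 per week, each lasts 7 days, and a dose is modified if an event is active on the dosing day. The days on which an onset would lead to a modification are 3 × 7 = 21 in Arm A (the three infusions after the first), 8 × 7 = 56 in Arm B for either drug, and 4 × 7 = 28 in Arm B for ipilimumab only.
- Arm A: 1 − exp(−0.05 × 21/7) = 1 − exp(−0.15) = 13.9%
- Arm B, either drug: 1 − exp(−0.40) = 33.0%
- Arm B, ipilimumab only: 1 − exp(−0.20) = 18.1%

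**After a split by drug.** In the per-dose model the ipilimumab row compares 4 infusions with 4, so the arms agree at equal risk (18.5% in each at q = 5%). The cross-check shows a small remaining imbalance, 13.9% against 18.1%. Arm A's first infusion is its first study dose and cannot be held for an earlier TEAE, whereas Arm B's first infusion follows the Week 1 injection. The numbers of infusions open to such a hold are 3 and 4. This gap is much smaller than 13.9% against 33.0%.

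**The case against.** A reader might infer that Arm B will show two or three times as many modifications without any added toxicity, and that the row is biased against Arm B. The documents do not support either statement.

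- **No rate is given.** The larger ratios need equal risk per dose and full exposure. The hold rules differ by drug: Protocol Table 3 has no dose modification for local or mild systemic reactions to IMO-2125, while Protocol Table 4 withholds ipilimumab for several toxicities. At 5% and 1% the ratio is 25.6/18.5, about 1.4. Stopping treatment early lowers both percentages.
- **The row is legitimate for the regimen.** Interrupted injections are a real burden of Arm B's assigned treatment. The row would mislead only if read as toxicity per dose, which the SAP does not claim. No test or decision rule is tied to it.
- **Context exists.** Exposure by drug, including the number of infusions received, is in Tables 14.3.1.1 and 14.3.1.2, which also go to the IDMC and topline. Discontinuation is split by drug, and the planned adverse-event listing shows action taken.
- **Pooling is inferred.** It follows from the absence of a drug name beside rows that have one. The mock displays are separate documents (SAP 3) and may already split the row.

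All four points stand as limits on size and wording. They do not supply the missing comparison: exposure tables do not attribute missed doses to adverse events, and a listing is not a summary by arm.

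**Conclusion.** The point holds as a low-cost improvement to a descriptive table; the plan contains no error here. One per-subject row covers 4 scheduled administrations in Arm A and 13, on 9 visits, in Arm B. It is therefore expected to be higher in Arm B whenever IMO-2125 doses are sometimes modified and the risk per ipilimumab dose is the same in both arms.

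The size is illustrative and rests on assumed rates with every dose reached: 18.5% against 37.0% to 48.7% at 5% per dose, narrowing to 18.5% against 25.6% if injections are modified 1% of the time. What the documents do establish is that the SAP describes no table comparing ipilimumab doses held for adverse events between arms. No endpoint, test or error rate changes, so the severity is minor.

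**What to change.** In SAP 11.2 and Table 14.3.2.1:

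1. Keep the present row and label it *any study drug*.
2. Add *TEAEs leading to ipilimumab interruption/reduction* for both arms, as the between-arm comparison.
3. Add *TEAEs leading to IMO-2125 interruption/reduction* for Arm B only.
4. Add a footnote that Arm A's first infusion is its first study dose, so 3 infusions in Arm A and 4 in Arm B can be held for an earlier TEAE.

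This follows the split the SAP already uses for discontinuation. The cost is two table rows and a footnote. SAP 8.2.7 refers to "action taken with both study drugs for the combination arm", which indicates that the action is already recorded by drug, so no new data should be needed. If the mock display already splits the row, only the SAP text needs to say so.

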- Subjects must be randomized within 28 days after signing the ICF; the first dose of study drug should be administered within 2 days after randomization.
- CBC and chemistries do not have to be repeated if Screening tests are completed within 7 days of start of treatment.
- PT, aPTT, INR.

8. Vital signs will include systolic and diastolic blood pressure, body temperature, pulse rate, body weight, and height (Week 1 only). Vital signs should be completed prior to treatment administration.
9. WOCBP only. Pregnancy test after randomization should be completed as deemed necessary by the Investigator or required by local law.
10. During the Follow-up Periods, for 90 days after the last dose of study treatment, all SAEs, irAEs, AEs Grade ≥ 3 , and associated concomitant medications for their treatment must be reported. For the remainder of the Follow-up Periods, AE reporting should be limited to Treatment-related Grade ≥ 3 AEs and SAEs, and the associated concomitant medications.
11. Optional (see Laboratory Manual).
12. To inform treatment management decisions, disease assessments are to be completed at Week 12 (± 1 week), then every 8 weeks (± 2 weeks) for the first year and every 12 weeks (± 2 weeks) during subsequent years.
13. To minimize bias in the PRO data, disease and PRO assessments are to be completed prior to study drug administration and AE evaluations at Weeks 1, 7, and 12 (± 1 week), then every 8 weeks (± 2 weeks) for the first year and every 12 weeks (± 2 weeks) during subsequent years.
14. Per institutional practices following the frequency of active follow-up disease assessments.
15. Follow-on anticancer treatment information will be collected during the telephone calls.
16. Serum samples will be collected for analysis of anti- ipilimumab antibodies; details are provided in the Laboratory Manual. Baseline sample to be collected at Week 1 before the first dose of study treatment.

Table 2: Schedule of Evaluations – Ipilimumab with IMO-2125 (Arm B)

Evaluation	Screening ¹	Combination Treatment ²							IMO Maintenance			Active F/up ³	Survival F/up ⁴
	Week	1	2	3	5	8	11	12	16	20	24		
Informed consent ⁵	X												
Inclusion/Exclusion	X												
Medical History	X												
ECOG	X	X			X	X	X		X	X	X		
CBC with diff	X	X ⁶	X	X	X	X	X		X	X	X	X ¹⁸	
Chemistry profile	X	X ⁶			X	X	X		X			X ¹⁸	
CH50/C3/C4 ⁷		X					X						
Coagulation ⁸		X							X				
Urinalysis		X							X				
Thyroid function tests		X			X	X	X		X			X ¹⁸	

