8.2. Duration of Study

8.2.1. Treatment Duration

The Treatment Phase of the study is 10 weeks for subjects assigned to Arm A and 24 weeks for subjects assigned to Arm B.

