9.3.4.2. Procedures for Assessment of Subjects with Changes in Complement Levels

Activation of complement in non-human primates is a well-described effect of phosphorothioate oligonucleotides, including IMO-2125. Monkeys are thought to be particularly sensitive to oligonucleotide-induced complement activation and a similar direct oligonucleotide-induced complement activation has not been observed in humans or other species.

Complement samples will be collected at Weeks 1 and 14 for Arm A and Weeks 1 and 11 for Arm B, according to the Schedule of Events table (see [Table 1](#)), and will be analyzed at a central laboratory (Medpace Reference Laboratories). If at any time during study participation, a subject experiences an acute drop in complement (total hemolytic complement assay, complement component 3, or complement component 4) levels $\geq 50\%$ or a drop to an absolute value below the lower limit of normal with reference to baseline testing or most recent values on study, the Sponsor will notify the site and the following procedures should be performed by the investigator:

1. Perform a safety evaluation and any necessary testing for the subject as clinically indicated.
2. If the results of the safety evaluations suggest any safety concerns associated with the drop in complement levels, hold the study drug treatment.
3. The patients should return to the clinic to have another serum sample drawn and sent to the central laboratory to confirm decreased complement levels.

Based on the results of this work-up and the subject’s disease assessment/response to study drug, the Investigator, in discussion with the Sponsor’s Medical Monitor, will determine the subject’s risk/benefit profile and discuss appropriate next steps regarding the subject’s continued treatment with study drug.

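### All-grade TEAE tables to Week 24 and to 12 months compare arms after required low-grade AE collection has ended 10 to 14 weeks earlier in Arm A

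*SAP*

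**What the plan says.** **Treatment length.** Protocol 8.2.1: "The Treatment Phase of the study is 10 weeks for subjects assigned to Arm A and 24 weeks for subjects assigned to Arm B". Under Protocol 9.3.3, Arm A receives ipilimumab "i.v. at Weeks 1, 4, 7, and 10" and Arm B receives IMO-2125 "8 mg intratumorally at Weeks 1, 2, 3, 5, 8, 11, 16, 20, and 24".

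**AE collection.** Protocol Table 1 footnote 10, repeated in Table 2 footnote 12 and Section 10.1: "During the Follow-up Periods, for 90 days after the last dose of study treatment, all SAEs, irAEs, AEs Grade" ≥3 must be reported. After those 90 days, reporting narrows to treatment-related Grade ≥3 AEs and SAEs. Section 10.1 permits this narrowing; the footnotes direct it. Section 10.1.2 goes further: after Active Follow-up, surveillance is passive and only SUSARs are recorded.

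**Analysis.** SAP 11 defines a TEAE by its start on or after first dose (or a worsening in grade after it) and sets no end to the window. SAP 11.2 then specifies:
- an onset table on one 21-day grid to Day 168, described as covering the treatment period, with each incidence divided "by the number of subjects who have not dropped out or died at the start of the onset interval";
- cumulative tables: "Cumulative TEAEs at 3, 6, 9, and 12 months from first dose will include all TEAEs with a start date" on or before the cut-off. No denominator is stated there.

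SAP 7 reports summaries by study arm unless stated otherwise. In SAP 16.2 the onset table is marked for the ORR and Final analyses. The cumulative treatment-related tables are marked for the IDMC and Final, and the cumulative all-TEAE tables for Final.

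**The concern.** A subject whose Grade 1-2 events no longer have to be recorded is not at risk of a recorded Grade 1-2 event. The onset table nevertheless keeps that subject in the risk set unless he or she has dropped out or died. Progressed subjects in Survival Follow-up have done neither, so they stay in as well. Because full collection stops earlier in Arm A by design, equal true rates would appear as a late excess in Arm B. The distortion runs against the combination, and the cumulative treatment-related tables go to an IDMC that weighs benefit against risk (Protocol 8.1.2).

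**Working it through.** **1. The plan's own grid.** Interval k runs from Day 21(k−1)+1 to Day 21k. For k = 8 this gives Day 148 to Day 168, as SAP 11.2 states.

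**2. Key days.** With first dose on Day 1, Week w starts on Day 7(w−1)+1.
- Arm A last planned dose, Week 10: Day 64. Adding 90 days gives Day 154.
- Arm A Week 14 visit: Day 92. Table 1 places it under the Treatment Period, and Protocol 9.3.4.2 uses it: "Complement samples will be collected at Weeks 1 and 14 for Arm A".
- Arm B last planned dose, Week 24: Day 162. Adding 90 days gives Day 252.

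Full collection in Arm A therefore ends (162−92)/7 = 10 weeks or (162−64)/7 = 14 weeks before Arm B's, depending on whether the Week 14 visit or the last dose ends it. The documents do not settle which.

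**3. Days of required all-grade collection per interval, all planned doses given.**

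| Interval | Days | Arm A, to Week 14 | Arm A, to last dose | Arm B |
|---|---|---|---|---|
| 1-3 | 1-63 | 21/21 each | 21/21 each | 21/21 each |
| 4 | 64-84 | 21/21 | 1/21 | 21/21 |
| 5 | 85-105 | 8/21 | 0/21 | 21/21 |
| 6, 7 | 106-147 | 0/21 each | 0/21 each | 21/21 each |
| 8 | 148-168 | 0/21 | 0/21 | 15/21 |

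**4. Share of each cumulative window under required all-grade collection.** The SAP's cut-off is first dose date + x(365.25/12), so the windows hold 92, 183, 274 and 366 days.

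| Window | Arm A, to Week 14 | Arm A, to last dose | Arm B |
|---|---|---|---|
| 3 months | 92/92 = 100% | 64/92 = 70% | 100% |
| 6 months | 92/183 = 50% | 64/183 = 35% | 162/183 = 89% |
| 9 months | 92/274 = 34% | 64/274 = 23% | 162/274 = 59% |
| 12 months | 92/366 = 25% | 64/366 = 17% | 162/366 = 44% |

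**5. Events collected alike.** With all planned doses given, SAEs, irAEs and Grade ≥3 AEs must be reported in both arms to Day 154. Arm A's requirement then narrows from Day 155, Arm B's only from Day 253.

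**6. Illustration under stated assumptions.** None of these values is in the documents: equal true rates, 10% of subjects per 21 days; a share s of events Grade 1-2, non-serious and non-immune-related; half of the rest treatment-related; sites report only the minimum; Week 14 reading. With F days of full collection, R days in the 90-day tier and T days after it,

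recorded incidence = 1 − 0.9^(E/21), where E = F + (1−s)R + 0.5(1−s)T.

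- Interval 6 or 7, s = 0.7: Arm A has E = 0.3×21 = 6.3, giving 3.1%; Arm B has E = 21, giving 10.0%.
- 6 months, s = 0.7: Arm A has E = 92 + 0.3×62 + 0.15×29 = 114.95, giving 43.8%; Arm B has E = 162 + 0.3×21 = 168.3, giving 57.0%.

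| Arm A vs Arm B | s = 0.5 | s = 0.7 | s = 0.9 |
|---|---|---|---|
| 3 months | 37.0% vs 37.0% | 37.0% vs 37.0% | 37.0% vs 37.0% |
| Intervals 6, 7 | 5.1% vs 10.0% | 3.1% vs 10.0% | 1.0% vs 10.0% |
| Interval 8 | 3.5% vs 8.6% | 2.1% vs 8.1% | 0.7% vs 7.5% |
| 6 months | 48.0% vs 57.9% | 43.8% vs 57.0% | 39.3% vs 56.1% |
| 12 months | 58.6% vs 69.3% | 51.1% vs 64.4% | 42.1% vs 58.8% |

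On the last-dose reading with s = 0.7, the 3-month table also separates, at 30.5% vs 37.0%.

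**The case against.** - **Only one arm is being dosed late.** After Week 10 Arm A is off treatment, while Arm B receives IMO-2125 at Weeks 11, 16, 20 and 24. A real late excess is expected in Arm B. A reader might infer that the reporting rule creates the whole late difference; the documents do not support that. What stands is that the tables cannot divide the real part from the artefact.
- **Much remains collected.** irAEs of any grade must be reported for 90 days after the last dose, from a broad list, and SAP 11.5 adds sponsor review across 17 organ classes. The stated classes are also a minimum, so sites may record more. A reader might infer that late Grade 1-2 rates in Arm A fall to about zero, or that control-arm toxicity is understated in general. Neither follows: the loss up to Day 154 is confined to Grade 1-2, non-serious, non-immune-related events. Voluntary extra reporting makes collection uneven, however, not equal.
- **Serious events can be read separately.** The cumulative tables split by maximum grade, and serious, immune-related and Grade ≥3 events have their own tables. This limits the harm but does not correct the low-grade and any-grade figures.
- **The onset table is labelled as covering the treatment period.** That could be read as ending Arm A's rows at its own treatment period. Neither the interval list nor the denominator says so, and the cumulative tables carry no such label.
- **The analyses are descriptive.** No test or alpha is involved, and the artefact cannot hide toxicity of the combination. Safety conclusions still rest on these by-arm percentages, and SAP 9.5 shows awareness of the collection tiers by building them into the definition of a concomitant medication.

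**Conclusion.** The point holds in limited form. Arm A's recorded incidence of Grade 1-2, non-serious, non-immune-related TEAEs is understated relative to Arm B's from interval 5 on if full collection runs to the Week 14 visit, and from interval 4 if it ends at the last dose. The 6-, 9- and 12-month tables are affected on both readings; the 3-month table only on the second. Intervals 1 to 3 are sound for subjects still on treatment.

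Required collection of SAEs, irAEs and Grade ≥3 AEs is equal to Day 154. This assumes that all planned doses are given and that the footnotes, rather than the SUSAR-only rule, govern subjects in Survival Follow-up. It then narrows earlier in Arm A.

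The coverage figures follow from the documents. The size of the distortion does not: it depends on the low-grade share, which is not given, and on how much sites report beyond the minimum. The percentages in the illustration show a mechanism and are not a forecast.

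**What to change.** 1. State when full AE collection ends in Arm A: at the last dose or at the Week 14 visit. Reconcile the three statements on later reporting: Protocol 10.1 (narrowing permitted), the Table 1 and Table 2 footnotes (narrowing directed) and Protocol 10.1.2 (SUSARs only after Active Follow-up).
2. In the interval table, count in the denominator only subjects still under full AE collection at the start of the interval. Footnote that this conditions on remaining in that period.
3. Limit by-arm all-grade comparisons to the common full-collection window from first dose, to about Day 64 or Day 92 depending on item 1. Show later all-grade data for Arm B as descriptive only.
4. Beyond that window, compare arms only on SAEs, irAEs and Grade ≥3 TEAEs over a common window from first dose, to Day 154. A rule of 90 days from each arm's last dose would again give unequal windows, Day 154 against Day 252. Restrict later cumulative comparisons to treatment-related Grade ≥3 AEs and SAEs as collected in both arms.

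Cost: SAP wording and minor reprogramming of the onset and cumulative tables, with no new data. The late all-grade comparison between arms is lost.
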